10.3 Planned Analyses

10.3.1 Datasets to be analysed, analysis populations

All patients meeting inclusion/exclusion criteria and randomized will be included in the analysis. The efficacy analysis will be performed first on an 'intention-to-treat' (ITT) basis followed by on a 'per-protocol' (PP) basis (definitions provided below).

- The intention-to-treat population (ITT) is based on the initial treatment allocation.
- The per-protocol population (PP) is based on the treatment the patients actually received according to the protocol

An overview of the number of patients enrolled in the study will be presented in a flow chart that will indicate the eligibility for the various analysis populations.

All recorded and derived variables will be presented according to the categories of treatment group and examination time points using appropriate descriptive summary tables. Adverse events with onset after initiation of the study treatment will be displayed in summary tables.

Baseline characteristics will be compared between the treatment groups by means of descriptive statistics and standardized differences. Prognostic factors suspected to be unbalanced between the groups will be taken into account during the analyses.

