8.3 Crossover

An optional bi-directional cross-over into the other intervention group (experimental or control) is possible after follow-up examination at the time-point T2 (3 months after the beginning/6 weeks after the end of the intervention) in the case of subjectively unsatisfying result despite completion of the originally assigned intervention.

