9. STUDY ASSESSMENTS

9.1 Study flow chart(s) / table of study procedures and assessments

After the patient signed the informed consent they will be allocated in the EMS treatment group or control group by a block randomization procedure.

Each patient (treatment and control group) get a one hour training lesson three times per week during the intervention period of 6 weeks .

The primary endpoint will be measured 3 months after the intervention period has been finished. Afterwards the mentioned optional cross-over in the other group is allowed in the case of subjectively unsatisfying result despite completion of the originally assigned intervention. In this case the study will get one appointment more (4.5 months after patient has been included).

The next time points will be 6 and 12 months after therapy finished.

There will be a measurement of the ROM and different strength parameters at each follow-up appointment (time needed: 30min). Additionally there will be a questionnaire to fill out by the patients to get the subjective parameters (time needed. 30min). Furthermore there will be recorded video from the patient (anonymized; from the backside) to visualize the movement pattern. Optional the patient can hand over a video from his main sport activity (anonymized) to the study coordinator. Both videos will upload into the data base for quality evaluation.

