11.1.3 Imaging data

Imaging data of the participants will be collected and stored at each study center locally as part of the clinical routine when screening the eligibility of the patients. In the final monitoring process, all collected imaging data will be evaluated at each study center and exported as pseudonymized data.

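### Section 10.3.1 lets the set labelled ITT omit randomised patients later judged ineligible, and words the per-protocol set so that it reads as as-treated

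*Protocol*

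**What the plan says.** Protocol section 10.3.1 announces that it defines the analysis sets. It contains four relevant statements:

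- Entry to the analysis: "All patients meeting inclusion/exclusion criteria and randomized will be included in the analysis".
- Order: "The efficacy analysis will be performed first on an 'intention-to-treat' (ITT) basis followed by on a 'per-protocol' (PP) basis".
- ITT: "The intention-to-treat population (ITT) is based on the initial treatment allocation".
- PP: "The per-protocol population (PP) is based on the treatment the patients actually received according to the protocol".

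Other sections bear on how these would work in practice:

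- Section 9.1 places allocation after consent: "After the patient signed the informed consent they will be allocated in the EMS treatment group or control group by a block randomization procedure". Table 1 lists the eligibility check and randomisation at the same screening visit.
- Section 6.2 says that patients cannot be blinded and that examiners need not be.
- Section 8.3 opens crossover, in either direction, only after the 3-month visit (T2), "in the case of subjectively unsatisfying result despite completion of the originally assigned intervention".
- Section 11.1.3, on the imaging used for screening, says: "In the final monitoring process, all collected imaging data will be evaluated at each study center and exported as pseudonymized data".
- Section 10.3.3 makes all secondary analyses explorative.

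**The concern.** **ITT.** The opening sentence sets two conditions, being randomised and meeting the criteria. The ITT bullet settles which arm a patient counts in. It does not say that every randomised patient is kept. Read together, the two statements describe a modified ITT set under an ITT label. Several exclusion criteria in section 7.1 are imaging readings (glenoid retroversion, decentering, any visible cartilage damage) on which two readers can differ. If eligibility were questioned after randomisation, nothing in the protocol requires the decision to be made blind to arm and outcome. Omissions made by staff who know both could favour one arm in the primary analysis.

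**PP.** Grouping by treatment received is the usual definition of an as-treated set. A per-protocol set normally keeps patients in their randomised arm and drops those who departed from the protocol. The difference matters here because crossover is a protocol-permitted step triggered by a poor result. A patient who crosses over has arguably received the second treatment in line with the protocol. If that patient is then counted under the second treatment at 6 and 12 months, group membership depends on the earlier outcome.

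**Working it through.** **1. The plan's own sample size (section 10.2).** Effect size = 10.4 / 13 = 0.8. A two-sided two-sample t-test at alpha 0.05 and 80% power needs 25.52 per arm, so 26 per arm and 52 in total, as stated. Drop-out: 52 / 0.80 = 65, against 66 stated (33 per arm). Screening: 66 / 0.75 = 88, as stated. The figures reproduce.

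**2. Does keeping every randomised patient cost power?** At an effect size of 0.8, power is 80.7% with 52 analysed and 89.3% with 66. The issue is possible bias and labelling, not power.

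**3. Where each statement can act.**

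| Set | 3 months (primary) | 6 and 12 months (exploratory) |
|---|---|---|
| ITT as worded | Can lose patients judged ineligible; cannot swap them between arms | Same |
| PP as worded | Affected only by wrong or incomplete treatment in the first 6 weeks; crossover has not opened | Could count crossover patients under their second treatment |

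**4. Illustration for leaving patients out.** The documents give no rate of ineligible patients. Assumptions: no true effect, SD 13 (section 10.2), 33 per arm, and k patients in each arm whose WOSI is 1 SD (13 points) worse. Only one arm loses its k patients. Shift in the mean difference = 13k / 33:

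- k = 2: 26 / 33 = 0.79 points
- k = 4: 52 / 33 = 1.58 points

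Simulated two-sided rejection (5,000 runs each) was 4.8% and 6.8%. With all patients kept as allocated it stayed below 5%. As a harsher case, omitting 3 of 26 patients who lie 1 SD below their arm mean moves that mean by 3 × 13 / 23 = 1.70 points, which is 16% of 10.4.

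**5. Illustration for moving patients (treatment-received grouping).** Same assumptions, but the k patients from one arm are counted in the other. Shift = 13 × 2k / (33 + k):

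- k = 2: 52 / 35 = 1.49 points
- k = 4: 104 / 37 = 2.81 points

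Simulated rejection was 6.8% and 12.2%.

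**6. Illustration for selection at 6 and 12 months.** Assume that 30% of one arm cross over. If crossover follows WOSI exactly, the mean of the remaining 70% rises by φ(0.524) / 0.70 = 0.497 SD, and 0.497 × 13 = 6.46 points. At a correlation of 0.5 it rises by 3.23 points. This is a shift in **one arm's mean**, from removal alone. The shift in the contrast is the difference between the two arms' shifts, so it is zero if both arms lose patients in the same way and up to 6.46 if only one does. Moving patients rather than removing them also changes the receiving group, by an amount that depends on the effect of the second course. The documents do not give that effect.

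**The case against.** The strongest reply is that the opening sentence is only descriptive: patients are screened, found eligible, randomised and analysed. Eligibility is settled at the screening visit, section 10.3.1 contains no rule for removing anyone, and section 8.4 recognises no ground for withdrawing a patient. ITT comes first and follows initial allocation. This stands in so far as late exclusions may be few and none is planned. It does not supply the missing statement that all randomised patients are kept.

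A reader might infer that centres will reopen eligibility from the images at the end, with outcomes in hand, and drop patients accordingly. The documents do not support that. Section 11.1.3 has the images evaluated and exported; it mentions neither an eligibility decision nor removal. Section 11.3 limits each site to its own data, so a centre may know its own patients' scores but not the pooled comparison. The criteria also rest on pre-treatment imaging, and exclusion on such criteria need not bias the result if done objectively and blind. The protocol simply does not require blinding.

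A reader might also infer that the PP set definitely counts crossover patients under their second treatment. No passage says so, and the closing words of the PP bullet leave its meaning open. The absence of a completion threshold or a list of major deviations is not a fault either, because such detail is commonly left to the statistical analysis plan. What remains is that the protocol states a basis for PP, and the basis it states is treatment received.

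Finally, every shift above comes from chosen inputs. That is correct, and they show direction and range only.

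**Conclusion.** The point holds as a badly stated rule. Followed as written, the set labelled ITT need not contain all randomised patients, and the set labelled PP is close to as-treated. The ITT weakness reaches the primary analysis, but only through omission of patients later judged ineligible, which the protocol permits without planning. Arms in that analysis cannot swap members. The crossover part is confined to the second-line set at exploratory 6- and 12-month endpoints, because crossover opens after the primary endpoint visit; section 6.1 itself accepts that heavy crossover would put only secondary endpoints at risk.

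Under the assumed inputs, the effect on the primary contrast is about 0.8 to 1.6 points, small beside 10.4. The effect of crossover selection could be larger if crossover is mostly one-way, and could cancel if it is balanced. The protocol gives no rate of ineligibility or crossover, so none of these figures is a forecast. The correction is worth making because it costs almost nothing and protects the label on the primary analysis.

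**What to change.** Amend section 10.3.1 as follows:

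1. **ITT:** all randomised patients, analysed in the arm to which they were allocated, whatever is later found about eligibility. Exclusion of ineligible patients is a sensitivity analysis only.
2. **PP, for the 3-month endpoint:** patients who completed the assigned course without major deviation, analysed in their randomised arm, with membership fixed before outcomes are reviewed. Section 8.4 already has the interventions logged in the database, so membership can be determined.
3. **6 and 12 months:** compare the randomised arms as strategies that include optional crossover, keeping data after crossover. Dropping those data would remove dissatisfied patients from their own arm and recreate the selection described above. Crossover patients can be described separately.
4. **Any analysis by treatment received:** label it as-treated and treat it as supportive.

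The cost is a wording change. The sample size stays at 66 randomised. The downside is that a few ineligible patients may slightly dilute the ITT effect: if, for illustration, 2 of the 33 patients in the EMS arm could not benefit at all, the expected difference would fall from 10.4 to 10.4 × 31 / 33 = 9.8 points.

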10.3.2 Primary Analysis

The analysis of the primary outcome parameter (WOSI at 3 months) will be performed using an independent sample T-Test or linear regression with WOSI as the dependent variable and treatment intervention and baseline factor(s) as the independent variable depending on the need for statistical adjustment. The strength of effect will be presented as the mean group difference along with its 95% confidence interval. A random-effect model will be used to account for center effect.

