6.2.1 Randomisation

A randomization sequence will be generated electronically using Stata (StataCorp LP, Texas USA) separately for each participating centers for up to X patients and loaded within an online study database in REDCap² (Research Electronic Data Capture) for automatic concealed allocation. Block-randomization with blocks of 2 and 4 will be used to minimize the risk of unequal group sizes. The randomization process allows to divide the study participants into two cohorts of comparable characteristics. We will compare these cohorts with regards to potential confounding factors before the outcome analyses and adjust statistically for any observed imbalance as appropriate.

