10.2 Determination of Sample Size

The calculated sample size for a power of 80%, an alpha error probability of 5%, and an estimated effect size of 0,8 is 52. The effect size was calculated according to Cohen by dividing the minimally clinically important difference of the WOSI (10,4%) by the expected standard deviation of the WOSI among the study participants (13%) based on the pilot trial results. The software used to calculate the sample size was G*Power (HHU Duesseldorf, Duesseldorf, Germany). When accounting for an expected drop-out rate of approximately 20% due to non-compliance or loss to follow-up 66 patients need to be assigned to the trial. Due to the strict exclusion criteria with an expected exclusion rate of 25% approximately 88 patients need to be assessed for eligibility.

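### Observed baseline imbalance decides the primary WOSI model; one pre-specified model with baseline WOSI and centre would restore the nominal level and add precision at no cost

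*Protocol*

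**What the plan says.** Protocol 10.3.2, repeated in the synopsis, allows two primary analyses of WOSI at 3 months. One is an independent-samples t-test. The other is a linear regression with treatment and "baseline factor(s) as the independent variable depending on the need for statistical adjustment". The factors are not named.

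Two other sections say how the need is established. Section 6.2.1 has the arms compared on potential confounders and the team then "adjust statistically for any observed imbalance as appropriate". Section 10.3.1 gives the measure: "Baseline characteristics will be compared between the treatment groups by means of descriptive statistics and standardized differences". It then adds: "Prognostic factors suspected to be unbalanced between the groups will be taken into account during the analyses". Neither section gives a cut-off.

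On centre, 10.3.2 closes with "A random-effect model will be used to account for center effect". Section 6.2 promises adjustment for clustering within centres, and 6.2.1 generates a separate randomisation sequence for each centre.

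Section 9.2.1 records questionnaires at the screening/baseline visit, so a baseline WOSI should be available.

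**The concern.** The choice of primary model, and of the covariates in it, depends on a preliminary look at the same data. The standard error of a t-test assumes that chance baseline differences are free to vary. Under this rule the t-test is kept only when those differences happen to be small, so its standard error is then too large for the trials in which it is used. The reported p-value and 95% confidence interval no longer have their nominal properties.

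A strong baseline predictor is also useful whether or not it is imbalanced, because it removes residual variance. Making its use depend on imbalance discards that gain in most trials. This is the trial's only confirmatory comparison (10.3.3 calls all secondary analyses explorative), and it is planned on 52 evaluable patients.

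Finally, a two-sample t-test has no place for a centre term, so one of the two permitted analyses does not honour the centre adjustment promised in 6.2 and 10.3.2.

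**Working it through.** **Inputs from the protocol (10.2, 6.2).** Difference 10.4%, SD 13%, power 80%, alpha 5%, allocation 1:1, total 52.

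**Assumed, because the protocol gives no value.** Correlation r between baseline and 3-month WOSI: 0.3, 0.5 or 0.7. Cut-off on the standardised difference: 0.1 to 0.5.

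**1. The plan's own figure.** The protocol states: "The calculated sample size for a power of 80%, an alpha error probability of 5%, and an estimated effect size of 0,8 is 52". With d = 10.4/13 = 0.8 and 26 per arm, the noncentrality is 0.8 × √(26/2) = 2.88 on 50 degrees of freedom. The two-sided 5% t-test then has power 80.7%. The stated 52 is reproduced, and it is the sample size of an unadjusted two-sided t-test.

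**2. Always adjusting for baseline WOSI.** Residual SD = 13 × √(1 − r²).

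| r | Residual SD | Effective d | Power, 26 per arm | Total N for 80% |
|---|---|---|---|---|
| 0.3 | 12.40 | 0.84 | 84.3% | about 48 |
| 0.5 | 11.26 | 0.92 | 90.4% | about 40 |
| 0.7 | 9.28 | 1.12 | 97.7% | about 28 |

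**3. How often the rule adjusts.** With 26 per arm and a cut-off of 0.25, the standardised difference passes the cut-off when |Z| > 0.25 × √13 = 0.90, a probability of about 0.37. In roughly 63% of trials baseline WOSI would therefore stay out of the model.

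**4. The rule itself, by simulation.** The set-up is 26 per arm and one normally distributed baseline covariate. ANCOVA is used if the absolute standardised difference exceeds the cut-off, and a t-test otherwise. There were 200,000 trials under no effect and 40,000 at d = 0.8. Entries are for r = 0.3 / 0.5 / 0.7.

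| Analysis | Type I error (%) | Power (%) |
|---|---|---|
| Rule, cut-off 0.1 | 4.6 / 4.3 / 3.8 | 82.8 / 87.9 / 94.7 |
| Rule, cut-off 0.2 | 4.6 / 3.9 / 3.0 | 82.6 / 86.3 / 91.5 |
| Rule, cut-off 0.25 | 4.5 / 3.7 / 2.7 | 82.0 / 85.2 / 90.1 |
| Rule, cut-off 0.5 | 4.7 / 4.3 / 3.2 | 81.0 / 82.0 / 83.4 |
| ANCOVA always (run with cut-off 0.25) | 4.9 / 5.0 / 5.0 | 83.7 / 89.9 / 97.3 |
| t-test always (same run) | 4.9 / 5.0 / 5.0 | 81.0 / 80.7 / 81.1 |

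A separate simulation at cut-off 0.25 gave type I error 4.6%, 3.6% and 2.7%, and power 82%, 85% and 90% against 83%, 90% and 97% for ANCOVA. These agree closely with the table.

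**5. Reading.** Under every cut-off the type I error is below 5% and the power lies between the t-test and ANCOVA, never below 80%. At cut-off 0.25 the power forgone is 83.7 − 82.0 = 1.7 points at r = 0.3, 89.9 − 85.2 = 4.7 at r = 0.5 and 97.3 − 90.1 = 7.2 at r = 0.7.

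The simulations contain no centre term, so they put no size on the centre point. That point rests on the wording alone.

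**The case against.** The strongest defence is that the rule does no harm to the error rate and meets its power target. That stands: the type I error is below nominal throughout, and power is at least 81% in every scenario. The loss is efficiency, and its size depends on a correlation and a cut-off that the protocol does not give.

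A second defence is that covariate lists and thresholds belong in a statistical analysis plan, which is not at hand. This stands in part. Section 10.3.2 names no factors and does not exclude baseline WOSI, so it is an inference that baseline WOSI enters only when imbalanced. But the protocol does not simply leave the matter open. Three sections tie adjustment to imbalance, and an analysis plan faithful to them would inherit that rule.

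On centre, the random-effect sentence is unconditional, so naming a t-test beside it may be no more than loose wording. The two statements still need reconciling.

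Two stronger readings are tempting and should not be made.

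- A reader might infer that the open choice inflates the false-positive rate. That would require the model to be picked in the light of its result. Section 6.2.1 schedules the comparison of arms ahead of the outcome analyses, and no section proposes choosing by result.
- A reader might infer that baseline is undefined, or that a 0-week score given after unblinded allocation could serve as baseline. The synopsis lists baseline at inclusion separately from 0 weeks, and 9.2.1 designates the screening day as baseline. Table 1 is too damaged in the available text to show which marks belong to WOSI. What remains is narrow: Table 1 puts randomisation at the screening visit, and 9.1 says "After the patient signed the informed consent they will be allocated in the EMS treatment group or control group", without saying that the questionnaire comes first.

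**Conclusion.** The point holds as one of calibration and efficiency. The imbalance-triggered choice makes the primary test conservative, with type I error of roughly 2.7% to 4.7% over the correlations and cut-offs examined. It also gives up part of the precision that baseline WOSI could supply. The loss is small if the correlation is near 0.3 and appreciable if it is near 0.7. The results assume one normally distributed covariate, equal arms of 26 and no centre effect.

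The stated sample size is correct for an unadjusted two-sided t-test and need not change. Separately, the t-test option is incompatible with the promised centre adjustment. Neither matter threatens the validity of a positive result, so this is a free improvement rather than a must-fix.

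**What to change.** Replace the model wording in 10.3.2, and its copy in the synopsis, with one primary model that applies whatever imbalance is observed: WOSI at 3 months on randomised arm and baseline WOSI, with centre as the randomisation stratum (either the random effect already stated or a fixed effect). Report the adjusted mean difference with its 95% confidence interval.

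For the primary analysis, delete the imbalance-triggered adjustment in 6.2.1 and 10.3.1. The descriptive baseline comparison can stay. Keep the unadjusted comparison as a sensitivity analysis.

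State that baseline WOSI is the score from the screening/baseline visit in 9.2.1, completed before the allocation is released.

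The cost is protocol wording only, with no added patients or visits, since questionnaires are already recorded at that visit. The change should be made before outcome data are examined.

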10.3.3 Secondary Analyses

All secondary analyses will be explorative. Secondary outcome variables will be analyzed using univariable random-effect logistic (categorical variables) or linear (continuous variables) regression. Multivariable regression will be conducted depending on the need for adjustment of baseline prognostic factors. Significance level is set to 0.05.

10.3.3.1 Safety analysis

Based on the complication-free pilot trial, no adverse events are pre-specified but continuous recording of unexpected adverse events will be executed in both treatment arms. In the case that adverse events are recorded, the independent expert group and ethical committee supervising the trial will be informed and may decide whether the trial can be continued or must be stopped.

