	- WOSI (Western Ontario Shoulder Instability Index)					
	Secondary Parameter:					
	 SSV (Subjective Shoulder Value) ROM Strength measurement (Flexion/Abduction/Rotation) Impairment of daily activities Sports impairment Pain level Satisfaction level with treatment 					
Study design:	Prospective, randomized, controlled, optional crossover study					

Inclusion / Exclusion criteria:	Key inclusion criteria: - Non-controllable positional functional posterior shoulder instability
	 Key exclusion criteria: < 14 years multidirectional instability static posterior instability/migration connective tissue disease degenerative joint disease structural defects visible on pre-treatment MRI Any acquired glenoid bone defect Glenoid dysplasia with more than 10° of retroversion (of cartilagineous surface) according to Imhoff et al.⁷ Convex cartilagineous glenoid articular surface Static posterior glenohumeral decentering >55% according to Walch et al.¹⁸ Degenerative changes (any visible cartilage damage or OA) neurological disorder or nerve injury existing pain syndrome (defined by pain at rest or during motion which is not caused by dislocation but impedes physiotherapeutic training and/or EMS) non-tolerance of EMS treatment (e.g. cardiac pacemaker) previous participation in a pathology-specific standardized EMS or physiotherapy protocol
Measurements and procedures:	Follow-up per patient (time after start of the treatment) : Baseline (Inclusion), 0 weeks (Start treatment), 6 weeks, 3 months, 6 months and 12 months Duration of intervention per patient : 6 weeks
Study Product / Intervention:	Experimental intervention: electrical muscle stimulation based therapy protocol
Control Intervention (if applicable):	Control intervention : conventional state-of-the art physiotherapy protocol
Number of Participants with Rationale:	There will be a total of 88 patients included. Rationale: See Statistical Considerations
Study Duration:	30 months
Study Schedule:	01/20 First-Participant-In (planned) 07/22 Last-Participant-Out (planned)

Study Centre(s):	It is a multicentric, multi-national study.					
	N=6 clinics					

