5.2 Secondary Outcomes

SSV: The Subjective Shoulder Value (SSV) is based on a single question that is answered subjectively the patients. The English formulation of this question is: "What is the overall percent value of your shoulder if a completely normal shoulder represents 100%?"¹

ROM

The following active and passive range of motion parameters will be documented:

Strength:

Abduction strength: The abduction strength (kg) is measured by 90° abduction in both shoulders (i.e. measured also for the opposite shoulder) using a spring balance (e.g. Pesola AG, Baar, Switzerland). The test is done with the patients standing. The arm should be abducted 90 degrees in scapula plane with the thumb showing upward. Only one measurement is performed.

Flexion strength: The flexion strength (kg) is measured by 90° flexion in both shoulders (i.e. measured also for the opposite shoulder) using a spring balance (e.g. Pesola AG, Baar, Switzerland). The test is done with the patients standing with thumb showing upward.

External rotation strength: The external rotation strength (kg) is measured with the arm in neutral rotation and the elbow flexed 90° in both shoulders (i.e. measured also for the opposite shoulder) using a spring balance (e.g. Pesola AG, Baar, Switzerland). The test is done with the patients standing with thumb showing upward.

Internal rotation strength: The internal rotation strength (kg) is measured with the arm in neutral rotation and the elbow flexed 90° in both shoulders (i.e. measured also for the opposite shoulder) using a spring balance (e.g. Pesola AG, Baar, Switzerland). The test is done with the patients standing with thumb showing upward.

Pain Level:

The pain level will be assessed with NRS (0 = no pain, 10 = worst pain).

Questions about impairment:

The patient will be asked about the impairment in daily activities, in the job and in sports activities (0% = no impairment, 100% = total restriction; 20% steps).

Satisfaction:

The patient will be asked about the level of satisfaction of the treatment (0% = not at all, 100% = complete satisfaction)

Characteristic of the subluxations

The patients will be asked about the subluxations events (e.g. first time, which movements) and previous treatments (e.g. surgery, physiotherapy).

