7. STUDY POPULATION

7.1 Eligibility criteria

All patients with FPSI will be included in this study irrespective of age, gender, degree of hyperlaxity, or duration of symptoms. Exclusion criteria focus on structural anomalies (static posterior migration, connective tissue diseases, degenerative joint diseases, structural defects) and other pathologies (multidirectional instability, neurological disorder or nerve injuries, existing pain syndrome, medical contraindication to EMS treatment) hindering, impeding, or prohibiting the complete administration of the control or experimental intervention. Additionally, patients with previous participation in a pathology-targeted standardized EMS or physiotherapy protocol are excluded in order to avoid patient's potential unwillingness to participate in or preformed mindset towards an intervention that they previously tried already without success. This combination of inclusion and exclusion criteria seems adequate to create a homogeneous group of study participants that still represents the typical characteristics of the majority of patients suffering from FPSI.

Participants fulfilling all of the following inclusion criteria are eligible for the study:

- Non-controllable positional functional posterior shoulder instability
- Informed Consent as documented by signature

The presence of any one of the following exclusion criteria will lead to exclusion of the participant:

- multidirectional instability
- static posterior instability/migration
- connective tissue disease
- degenerative joint disease
- structural defects visible on pre-treatment MRI
 - Any acquired glenoid bone defect
 - Glenoid dysplasia with more than 10° of retroversion (of cartilagineous surface) according to Imhoff et al.⁷
 - Convex cartilagineous glenoid articular surface
 - Static posterior glenohumeral decentering >55% according to Walch et al.¹⁸
 - Degenerative changes (any visible cartilage damage or OA)
- neurological disorder or nerve injury
- existing pain syndrome (defined by pain at rest or during motion which is not caused by dislocation but impedes physiotherapeutic training and/or EMS)
- non-tolerance of EMS treatment (e.g. cardiac pacemaker)
- previous participation in a pathology-specific standardized EMS or physiotherapy protocol for the affected shoulder
- Inability to follow the procedures of the study, e.g. due to language problems, psychological disorders, dementia, etc. of the participant,

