9.2 Procedures at each visit

9.2.1 Screening day/Baseline:

- Screening of the eligibility of the patients
- Collection of demographic data
- Recording of baseline data
 - Subjective data (Questionnaires)
 - Clinical Examination (ROM and strength measurement)
 - Anonymized video

9.2.2 Intervention visit 1 - 18

Intervention Visits 1 -18 (3 per week; 6 weeks)

- Execution of
 - 1h Intervention: EMS Therapy
 - 1h Control: Physiotherapy
- Acquisition of AEs

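### The default univariable analysis of strength gives the patient's own pre-treatment strength no fixed role, and adjusting only on imbalance leaves avoidable imprecision in place

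*Protocol*

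**What the plan says.** **Measurement.** Protocol section 5.2 defines four strengths (abduction, flexion, external and internal rotation), all in kg by spring balance and on both sides. For abduction it says: "The abduction strength (kg) is measured by 90° abduction in both shoulders (i.e. measured also for the opposite shoulder". Section 9.2 lists "Clinical Examination (ROM and strength measurement" among the baseline recordings at screening and again at the follow-up visits, so every patient should have a pre-treatment value.

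**Population.** Section 7.1 admits patients "irrespective of age, gender, degree of hyperlaxity, or duration of symptoms". The synopsis sets a lower age limit: "Key exclusion criteria: < 14 years multidirectional instability". Section 3.1 describes the condition as mainly one of teenagers and young adults.

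**Model.** Section 10.3.3 sets the default for every secondary outcome: "Secondary outcome variables will be analyzed using univariable random-effect logistic (categorical variables) or linear (continuous variables) regression". It continues: "Multivariable regression will be conducted depending on the need for adjustment of baseline prognostic factors". Section 10.3.1 says what prompts such adjustment: "Prognostic factors suspected to be unbalanced between the groups will be taken into account during the analyses". Section 6.2.1 likewise speaks of adjusting for imbalance that has been observed. Section 10.3.3 also labels all secondary analyses as exploratory.

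**The concern.** Absolute strength in kg differs between people for reasons unrelated to treatment: sex, age and body size. In a trial that enrols 14-year-olds and grown adults of both sexes, that variation goes into the residual variance of a model containing only treatment arm and a random effect. The patient's own screening value carries much of the same information and is already in the database.

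The protocol's rule for bringing it in is imbalance. That addresses chance differences between arms, not precision. When the arms are perfectly balanced the between-person spread is still in the residual, and the rule then leaves the univariable model in place. It also makes the covariate set depend on the baseline data.

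At stake is how informative the strength comparison can be. Besides range of motion, strength is the only listed efficacy outcome taken from a physician's examination rather than from the patient's own rating, in a trial where patients cannot be blinded.

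**Working it through.** **1. The plan's own figure.** Section 10.2 gives d = 10.4 / 13 = 0.8, 80% power and alpha 5%. A two-sided two-sample t-test (noncentral t) with 26 per arm has power 0.807, so the stated total of 52 is reproduced. Allowing for dropout, 52 / 0.80 = 65 against the stated 66; for screening, 66 / 0.75 = 88. I therefore use 26 evaluable per arm. This calculation is for WOSI; the protocol gives no SD, target difference or correlation for strength.

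**2. Unadjusted precision, in SD units of follow-up strength.**
- Standard error of the difference: SD × √(2/26) = 0.277 SD.
- 95% CI width: 2 × 2.009 × 0.277 SD = 1.11 SD.
- Difference detectable with 80% power: about 0.79 SD.

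**3. Effect of a baseline covariate.** If r is the correlation between screening and follow-up strength within arm, adjustment multiplies the residual variance by 1 − r² and the residual SD by √(1 − r²). An effect of d raw SDs is then tested as d / √(1 − r²). The degree of freedom spent on the covariate is ignored; with about 50 it is negligible.

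**4. Results for an assumed true difference of 0.5 SD, 26 per arm, two-sided 5%.**

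| r (assumed) | √(1 − r²) | CI width (SD) | Power | Equivalent sample-size factor, 1/(1 − r²) |
|---|---|---|---|---|
| unadjusted | 1.00 | 1.11 | 0.42 | 1.0 |
| 0.3 | 0.95 | 1.06 | 0.46 | 1.1 |
| 0.5 | 0.87 | 0.96 | 0.53 | 1.3 |
| 0.7 | 0.71 | 0.80 | 0.70 | 2.0 |
| 0.8 | 0.60 | 0.67 | 0.84 | 2.8 |

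The gain is small at r = 0.3, modest at 0.5 and large from about 0.7.

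**5. Does the imbalance rule recover this?** The factor √(1 − r²) does not depend on whether the arms happen to be balanced. With balanced arms the rule is not triggered, and the analysis stays on the unadjusted row.

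**The case against.** **It belongs in the SAP.** Covariates for one exploratory outcome are often left there, and the SAP is not shown. But section 10.3.3 does not leave the matter open: it names a default model and a condition for departing from it. An SAP that followed it would carry the same weakness.

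**Adjustment is already allowed.** True, so it would be wrong to call the planned analysis treatment-only. The point is narrower: adjustment is conditional, and on the wrong condition.

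**The form of the outcome is not fixed.** Also true. Section 10.3.3 does not say whether follow-up kg, change or a side-to-side measure is modelled, and section 11.2.4 provides for derived variables. A change score would use the baseline, but with equal variances its SD factor is √(2(1 − r)): 1.18 at r = 0.3, 1.00 at 0.5, 0.77 at 0.7 and 0.63 at 0.8. That is never better than the covariate model, and at r = 0.3 it is worse than ignoring baseline.

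**The correlation may be low.** If treatment restores stability in some patients and not in others, pre-treatment strength of an unstable shoulder may predict follow-up strength poorly. Nothing in the documents settles this, so the low values of r belong in the range.

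**Importance.** Section 5.1 argues that a comprehensive, valid objective measure cannot be had in this condition, and the protocol does not ask strength to confirm or contradict WOSI. This stands and limits the weight of the point.

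**Stronger readings that the documents do not support.** A reader might infer that body-size variation hides most of a real effect. It does not shrink the estimate, which is unbiased under randomisation; it widens the interval by an amount that depends on an unknown r. A reader might infer that patients of any age are compared; section 7.1 read alone suggests so, but the synopsis excludes those under 14. A reader might also infer that the opposite-shoulder readings go wholly unused, or that they would bring the gains tabulated. Section 10.3.1 promises descriptive summaries of all recorded variables, and the table concerns a single covariate, so any additional gain from the opposite side has not been calculated.

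**Conclusion.** The point holds as one of precision. The stated default omits the patient's own screening strength, and the trigger for including it does not address the loss. The direction of the gain is secure: for any appreciable correlation, the baseline-adjusted model is more precise than the univariable one.

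The size is not secure. It rests on an assumed difference of 0.5 SD, 26 evaluable patients per arm and an assumed r between 0.3 and 0.8; over that range power rises from about 0.42 to between 0.46 and 0.84. No bias is involved, the outcome is exploratory, and neither the WOSI analysis nor its sample size is touched. This is a free improvement rather than an error that threatens the trial.

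**What to change.** In section 10.3.3, state for each strength outcome that affected-side strength at follow-up is modelled on treatment arm, with the centre random effect and the screening affected-side value as a fixed covariate for every patient, regardless of observed imbalance.

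The screening opposite-shoulder value may be added as a second pre-specified covariate, though its extra contribution is not quantified here. A side-to-side ratio is less suitable as the main measure, because the opposite shoulder may also be affected.

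Cost: one sentence and one degree of freedom per model (two with the opposite shoulder). No new measurements or visits are needed.
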